### **13.3. Analysis of secondary outcomes**

Nominal variables will be evaluated in the same manner as the primary outcome. Continuous variables will be summarized (minimum, maximum, mean, standard deviation, median, lower and upper quartile) and the difference between groups will be tested by t-test or Wilcoxon-Mann-Whitney test as appropriate. For time-to-event outcomes, Kaplan-Meier will be used to estimate the survival curves and log-rank test will be used to test the difference between groups by ITT analysis.

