Data to be collected will consist of maternal age and ethnicity, gravida/para, gestational age, height, weight, estimated fetal weight, reason for induction, date and time of device placement, date and time of delivery, mode of delivery, Bishop score at eligibility assessment, Bishop score prior to dilator insertion, Bishop score after removal or expulsion of dilator, date and time of rupture of membranes, date and time of device expulsion/removal, hospital length of stay, other intrapartum and obstetrical interventions, complications in device placement and cervical ripening, during labor and delivery including but not limited to meconium, infections, hemorrhage, fetal decelerations and subject satisfaction. We will also collect the amount of analgesics subjects received during device placement, cervical ripening and induction time (includes acetaminophen or intravenous medications or regional anesthesia). Data will be abstracted from the medical records as well as from direct interview. We will also collect basic neonatal data including birth weight, Apgar scores, rate of admission to neonatal intensive care unit, infections, and other neonatal complications. The data collected will not be used for clinical diagnosis or treatment purposes. Additional economic data to be collected includes the following admission direct costs or charges from the following services/departments: Blood Bank Transfusion Operations, Chemistry Division, Hematopathology Division, JSH Labor & Delivery unit, Materials Management, Microbiology Division, Mother Baby Unit, Pharmacy, Respiratory Care Services, Surgical Operating Suite.

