### **6.2. Secondary Outcomes**

- Rate of vaginal deliveries (%)
- Rate of vaginal deliveries within 24 hours since admission to hospital (%)
- Rate of vaginal deliveries within 36 hours since admission to hospital (%)
- Time from hospital admission to reach active stage of labor defined as  $\geq 6$  cm (mins)
- Time from device placement to reach active stage of labor defined as  $\geq 6$  cm (mins)

- Change in Bishop score from insertion to extraction of device
- Change in cervical dilation after Dilapan-S®
- Rate of spontaneous vaginal deliveries after one round of cervical ripening (%) (no additional medical or mechanical interventions)
- Rate of operative vaginal deliveries (%)
- Rate of caesarean deliveries (%)
- Rate of artificial rupture of membranes (AROM) (%)
- Rate of epidural analgesia (%)
- Total duration of Dilapan-S® application (insertion to removal/extraction) (mins)
- Device placement to delivery interval (mins)
- Induction (Oxytocin/Prostaglandin initiation) to delivery interval (mins)
- Analgesia used during device placement (%), cervical ripening (%) and labor induction (%)
- Rate of adverse neonatal outcomes (composite and individual) –Apgar score <7 at 1-5-10 minutes, Cord arterial pH <7.1, neonatal ICU admission (%)
- Occurrence of maternal and neonatal complications within 2 weeks after delivery (%)
- Total duration of maternal hospital stay (hours)
- Subject reported clinical outcomes (sleep, rest, pain, activities of daily living, etc.) (Appendix 3)
- Subject reported satisfaction with Dilapan-S® treatment (Appendix 3)
- Medicaid charges for each hospitalized subject in both arms

*(Blood Bank Transfusion Operations, Chemistry Division, Hematopathology Division, JSH Labor & Delivery unit, Materials Management, Microbiology Division, Mother Baby Unit, Pharmacy, Respiratory Care Services, Surgical Operating Suite)*

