## 7. Inclusion and Exclusion Criteria

### 7.1. Criteria for Inclusion of Subjects:

Subjects must meet all of the inclusion criteria in order to be eligible to participate in the study.

Inclusion criteria are:

1. Pregnant woman whose plan of care is induction of labor
2. Maternal age between 18 and 45 years
3. Understanding and capable to sign informed consent
4. Singleton pregnancy
5. Gestational age  $\geq 37^{0/7}$  weeks  
(based on a sure last menstrual period or a first trimester dating ultrasound)
6. Live fetus in cephalic presentation
7. Intact membranes
8. Pelvic exam (sterile vaginal exam) of less than or equal to 3cm and at most 60% effaced

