## **13. Biostatistics/Sample Size**

Basic principles for an evaluation of the study are presented in this section, more detailed description of how to analyze collected data will be specified in statistical analysis plan (SAP) which will be written and approved before the database lock. The statistical analysis including the data from the additional site will be specified in the SAP.

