#### *Intent-to-treat Population (ITT)*

ITT includes all patients that were randomized into the study and primary outcome has been obtained. ITT subjects will be analyzed in accordance with their randomized study treatment (i.e. in the treatment group they were originally allocated, regardless of treatment actually received). ITT will be used for evaluation of the baseline characteristics and as the primary population for efficacy assessments. Other predefined subgroup interaction analysis for cervical dilation at randomization, parity ( $P=0$  vs  $P>0$ ), or  $BMI > 30 \text{ kg/m}^2$  will be also performed.

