### **13.4. Sample size**

Sample size was calculated based on the determination of superiority. The primary outcome is proportion of women with hospital stay >48 hours. For the sample size calculation, we assumed the proportion in the control arm would be 54% ( $p_i = 0.54$ ). This is based on current experience at UTMB and unpublished data from an international registry trial (9). We estimate that outpatient intervention would decrease this proportion by 30% ( $p_{ii} = 0.378$ ). Based on 85% power and two-sided alpha of 0.05, the total sample size per group required would be 169. Accounting for 10% of premature terminations or drop outs the sample size per group becomes 188, making the total sample size needed 376.

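### Baseline adjustment of the two cervical-change outcomes is a free but probably small gain in precision that the plan leaves unused

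*Combined protocol and SAP*

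**What the plan says.** Section 6.2 includes two outcomes that are differences from a baseline: "Change in Bishop score from insertion to extraction of device" and "Change in cervical dilation after Dilapan-S".

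Section 13.3 has one rule for continuous variables. They are summarized, and "the difference between groups will be tested by t-test or Wilcoxon-Mann-Whitney test as appropriate". It does not name the cervical outcomes separately, so the unadjusted comparison of raw change follows from the general rule.

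The data list in section 3 includes "Bishop score prior to dilator insertion, Bishop score after removal or expulsion of dilator". Insertion precedes randomization (sections 5.1 and 5.3), so the pre-insertion score is a true baseline. Section 3 lists no separate pre-insertion dilation item, but the dilation change in section 6.2 needs one.

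The only planned analytic use of baseline cervical status is in section 13.1, under the ITT population: "Other predefined subgroup interaction analysis for cervical dilation at randomization". Nothing in the document plans baseline adjustment. Section 13 describes itself as setting out basic principles and leaves further detail to a SAP to be approved before database lock; no separate SAP text is included.

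**The concern.** A two-sample test on raw change treats the post-removal value as if it rose by exactly one unit for each unit of baseline. If the true slope differs from 1, part of the baseline variation stays in the outcome. It widens the interval and lets a chance baseline difference between arms move the estimate. These are not two separate faults. They are the same variance term, seen once on average over randomizations and once in a single trial.

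The two outcomes are the ones closest to the ripening process itself. Times to 6 cm and to delivery, and mode of delivery, also depend on further ripening and oxytocin given at the clinical team's discretion (section 5.5). What is at stake is the width of the interval on two secondary outcomes, not the validity of any test.

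**Working it through.** **The plan's own figure.** The only design calculation is for the primary outcome (section 13.4): 54% against 37.8%, 85% power, two-sided alpha 0.05. The pooled normal formula without continuity correction gives 169 per group. Then 169/0.90 = 187.8, rounded up to 188, and 2 × 188 = 376. All three figures reproduce, and none depends on this point. No SD, correlation or power is stated for the cervical outcomes.

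**Formula.** Set the SD of the post-removal value to 1. Let r = SD(pre)/SD(post) and let rho be the pre-post correlation, both taken as equal in the two arms.

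- Variance of the change-score comparison: proportional to 1 + r² − 2·rho·r.
- Variance of the ANCOVA comparison: proportional to 1 − rho².
- Excess of the change score: (1 + r² − 2·rho·r) − (1 − rho²) = (r − rho)². This is never negative, and it is zero only when rho = r, that is, when the slope rho/r equals 1.
- Cost of estimating one slope at 169 per group: 1 + 1/(2 × 169 − 4) = 1.003, or about 0.3% of the variance.

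**Inputs.** The documents give neither r nor rho, so both are assumptions: r from 0.5 to 1.0, rho from 0.1 to 0.7.

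**Results.** Variance of ANCOVA divided by variance of the change score, with the reduction in CI width in brackets:

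| r | rho 0.1 | rho 0.3 | rho 0.5 | rho 0.7 |
|---|---|---|---|---|
| 1.0 | 0.550 (25.8%) | 0.650 (19.4%) | 0.750 (13.4%) | 0.850 (7.8%) |
| 0.75 | 0.701 (16.3%) | 0.818 (9.6%) | 0.923 (3.9%) | 0.995 (0.2%) |
| 0.5 | 0.861 (7.2%) | 0.958 (2.1%) | 1.000 (0.0%) | 0.927 (3.7%) |

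Two cells by hand: r = 1.0, rho = 0.1 gives 0.99/1.80 = 0.550; r = 0.5, rho = 0.3 gives 0.91/0.95 = 0.958.

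Simulation at 169 per group (3,000 runs per setting) agrees with the formula: 0.678 against 0.650 (r = 1, rho = 0.3), 0.751 against 0.750 (r = 1, rho = 0.5), 0.853 against 0.873 (r = 0.75, rho = 0.4), 0.975 against 0.958 (r = 0.5, rho = 0.3) and 1.001 against 1.000 (r = 0.5, rho = 0.5).

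**In terms of power.** Suppose the change-score test had 80% power at 169 per group. For rho of 0.3, 0.5 and 0.7, ANCOVA would have 93.5%, 89.9% and 86.0% at r = 1; 87.2%, 83.0% and 80.2% at r = 0.75; and 81.7%, 80.0% and 82.9% at r = 0.5.

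**Which row is likely.** Entry requires "Pelvic exam (sterile vaginal exam) of less than or equal to 3cm and at most 60% effaced". That restricts baseline values while leaving post-removal values free to spread, so the lower rows are more plausible than r = 1.

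**The case against.** The strongest reply is that section 13 gives basic principles only, that its test rule is generic and ends with a choice left open, and that a later SAP could add the adjustment. That is fair as to timing. It does not replace the method that is stated, which contains no covariate, and it makes the SAP the natural place for the change.

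The scores are also ordinal or coarsely recorded, so a rank test is defensible, and the variance formula above describes comparisons of means rather than a Wilcoxon test. This stands, and it is the reason to keep the rank test as a sensitivity analysis.

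Four stronger readings are tempting and are not supported:

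- *That the planned comparison is biased or has the wrong type I error.* Baseline is measured before randomization, so the raw comparison is unbiased and its error rate is nominal.
- *That a large loss is established.* The 0.55 figure needs equal SDs before and after ripening together with a correlation of 0.1. It is one corner of an assumed grid, and other cells show no loss at all.
- *That the entry limits push the slope below 1 and so worsen the loss.* Selecting on baseline does not lower the regression slope of post on pre. The loss equals Var(pre) × (1 − slope)², so a narrower baseline makes it smaller.
- *That the subgroup factor in section 13.1 has no data source.* Randomization comes after insertion and at least 30 minutes of observation (sections 5.1 and 5.4.1), and section 3 lists no examination at that moment. But the phrase can be read simply as baseline, and the text available here has nothing between sections 3 and 5. It merits a clarification at most.

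**Conclusion.** The point holds as a minor, free improvement. The plan collects a pre-randomization Bishop score and needs a pre-insertion dilation, yet uses each only by subtraction. ANCOVA costs about 0.3% of variance for the extra covariate and in large samples is otherwise never less precise.

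The size of the gain cannot be derived from the documents. Over the assumed range the variance ratio runs from about 0.55 to 1.00. With the baseline spread narrowed by eligibility it is probably near the upper end: 0.93 to 1.00 at r = 0.5 and rho of 0.3 to 0.7, which means intervals 0% to 4% narrower. This rests on similar SDs and correlation in both arms and on an approximately linear relation between pre and post values.

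Only two secondary outcomes are affected. The primary chi-square test and the sample size are untouched.

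**What to change.** In section 13.3 or the SAP, state that post-removal Bishop score and post-removal dilation will each be analysed by ANCOVA, with the pre-insertion value as covariate and arm as factor, and that the adjusted mean difference will be reported with its 95% CI. Keep the rank test on raw change as a sensitivity analysis.

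As an optional clarification, state in section 13.1 that the dilation subgroup factor means dilation at the pre-insertion examination.

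The cost is two or three sentences. No extra visits, data or participants are needed, because any woman with a change score already has the baseline value that the model uses.

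### Section 13.3 gives no rule for women delivered by caesarean before 6 cm; if they are censored, the Kaplan-Meier curves overstate the proportion reaching active labour

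*Combined protocol and SAP*

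**What the plan says.** Section 6.2 lists two secondary outcomes in minutes that end at 6 cm dilation: "Time from hospital admission to reach active stage of labor defined as" 6 cm or more, and "Time from device placement to reach active stage of labor defined as" the same threshold. Caesarean appears in the same list only as an outcome of its own, "Rate of caesarean deliveries".

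Section 13.3 offers two routes that could apply to an outcome in minutes. For continuous variables, "the difference between groups will be tested by t-test or Wilcoxon-Mann-Whitney test as appropriate". For outcomes of the time-to-event kind, "Kaplan-Meier will be used to estimate the survival curves and log-rank test will be used to test the difference between groups", by intention to treat. It assigns no named outcome to either route and gives no censoring rule. It mentions neither competing events nor women who never reach 6 cm.

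The opening of Section 13 describes the section as basic principles and leaves further detail to an analysis plan to be approved before database lock. The text available contains no such further detail on this point.

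**The concern.** Women enter the trial at 3 cm or less (Section 7.1), so every participant could be delivered by caesarean before 6 cm. Once that happens she cannot reach 6 cm. She is not a woman whose event was merely unobserved.

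Standard Kaplan-Meier practice would censor her at caesarean. The estimator then redistributes her weight to the women still in labour, as if she would have gone on to 6 cm as they did. A reader takes the resulting curve as the proportion of women in active labour by each hour, and it is too high for that purpose. Medians read from it are too early.

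The other route is no safer as written. A t-test or Wilcoxon test on minutes has no stated value for a woman who never reaches 6 cm. Analysing only those who did reach it selects on something that happens after randomisation.

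**Working it through.** **The plan's own figure.** The documents give no figure for time to 6 cm. The only calculated figure is the sample size for the primary outcome (Section 13.4), and it reproduces. With 0.54 against 0.378, two-sided alpha 0.05, 85% power and pooled variance:

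n = [1.960·√(2 × 0.459 × 0.541) + 1.036·√(0.54 × 0.46 + 0.378 × 0.622)]² / 0.162² = 168.4, so 169 per group.

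Then 169/0.90 = 187.8, so 188 per group and 376 in total. This does not bear on the present point.

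**Direction.** At each time t_j with d_j women reaching 6 cm and n_j at risk:

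- The Aalen-Johansen cumulative incidence rises by S(t_j−)·d_j/n_j, where S is the probability of having had neither event.
- 1-KM with caesareans censored rises by S₆(t_j−)·d_j/n_j, where S₆ ignores caesareans.

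S₆ is never below S, and it is strictly above S once a caesarean has occurred while others remain at risk. So 1-KM is too high whatever the caesarean rate. Only the size needs assumptions.

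**Size.** Inputs, all assumed: constant hazards, a median of 20 h to whichever event comes first (total hazard h = ln 2/20 = 0.03466 per hour), and a share c delivered by caesarean before 6 cm.

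- True cumulative incidence: (1 − c)(1 − e^(−ht))
- 1-KM with caesareans censored: 1 − e^(−(1 − c)ht)

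At t = 36 h, ht = 1.2477:

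| c | True proportion at 6 cm | 1-KM | Excess (points) |
|---|---|---|---|
| 10% | 0.642 | 0.675 | 3.3 |
| 15% | 0.606 | 0.654 | 4.8 |
| 20% | 0.570 | 0.631 | 6.1 |

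**Sensitivity to the assumptions.**

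- Constant hazards, 18 h median: the excess at 24 h / 48 h is 1.1 / 2.7 points at c = 5%, 3.1 / 7.6 at 15%, and 4.8 / 11.8 at 25%.
- Simulated lognormal times (median 18 h to 6 cm, caesarean median 12 to 26 h): the excess at 48 h is about 4–5 points at 5%, 10–14 at 15%, and 15–24 at 25%. It is larger when caesareans come earlier.
- Women with an early caesarean kept in the risk set to the end of follow-up as not reaching 6 cm: the excess is 0.

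**Comparison between arms (hypothetical).** Give both arms the same 6-cm hazard, 0.9 × 0.03466 = 0.03119 per hour, and let early caesarean be 10% in one and 20% in the other. 1-KM is 67.5% at 36 h in both. The total hazard in the second arm is 0.03119/0.80 = 0.03899, so its true proportion is 0.80 × (1 − e^(−1.4036)) = 60.3%, against 64.2% in the first. The gap of 3.8 points does not show on the Kaplan-Meier curves.

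**The case against.** The strongest reply is that the plan does not commit to the error. Section 13.3 never says that the 6-cm outcomes go to Kaplan-Meier, and it never says that caesareans are censored. A woman with an early caesarean can be kept in the risk set as never reaching 6 cm, and then there is no overstatement. Detail is also deferred to a later analysis plan. All of this stands, and it makes the overstatement conditional. It does not remove the gap, because the result depends on a rule that the text does not give.

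Second, other outcomes offer protection. Section 6.2 also lists the caesarean rate, the vaginal delivery rate, and vaginal delivery within 24 and 36 hours of admission. In the vaginal delivery rates a caesarean counts simply as not achieving the outcome, so an arm with more failed inductions should show there. This limits the consequences, but it does not correct a mislabelled curve.

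A reader might also infer more than the documents support:

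- *That one arm's curve is favoured.* No difference in early caesarean between arms is documented, and Section 5.5 makes management after the first 12 hours the same in both groups. With similar rates and timing, both curves shift by a similar amount. Nothing worked out here shows an arm with more failed inductions appearing faster.
- *That 90% against 80% reaching 6 cm would be hidden.* In the comparison above, those are the limits after unlimited follow-up. At 36 h the contrast is 64.2% against 60.3%.
- *That the log-rank test is invalid.* With caesareans censored it is a proper test of the cause-specific hazard. It does not test the proportion reaching 6 cm.

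**Conclusion.** The point holds in conditional form. Section 13.3 leaves open which outcomes are time-to-event and how caesarean before 6 cm is treated. If these women are censored, the curves for both 6-cm outcomes overstate the proportion reaching active labour.

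The direction follows from the estimators. The 3.3, 4.8 and 6.1 points at 36 h rest entirely on the assumed hazards, median and caesarean shares, and other assumptions give other sizes. Bias in the comparison between arms is possible but not shown.

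Two secondary outcomes are affected. The primary chi-square test in Section 13.2 and the sample size are not. The change is still worth making, because cumulative incidence directly estimates what readers will take from the curve, and the t-test or Wilcoxon route leaves the same women without a value.

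**What to change.** In Section 13.3 or the detailed analysis plan, before database lock:

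1. Name the time-to-event outcomes, including both times to 6 cm.
2. For those two, estimate the proportion reaching 6 cm by the Aalen-Johansen cumulative incidence, with caesarean before 6 cm as the competing event. If there is no other censoring, keeping these women in the risk set to the end of follow-up as not reaching 6 cm gives the same curve.
3. Keep the log-rank test, labelled as a comparison of cause-specific hazards, and add Gray's test as a complement. Which of the two leads is a choice of estimand and should be stated.
4. Do not analyse minutes only among women who reached 6 cm.

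The interval from device placement to delivery needs no such change, since caesarean is itself a delivery.

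The cost is a few sentences and a standard software routine. Date, time and mode of delivery are already on the data list in Section 3. The downside is slightly less familiar output.

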### **13.4. Sample size**

Sample size was calculated based on the determination of superiority. The primary outcome is proportion of women with hospital stay >48 hours. For the sample size calculation, we assumed the proportion in the control arm would be 54% ( $p_i = 0.54$ ). This is based on current experience at UTMB and unpublished data from an international registry trial (9). We estimate that outpatient intervention would decrease this proportion by 30% ( $p_{ii} = 0.378$ ). Based on 85% power and two-sided alpha of 0.05, the total sample size per group required would be 169. Accounting for 10% of premature terminations or drop outs the sample size per group becomes 188, making the total sample size needed 376.

## **14. Clinical Trial Registration**

This trial will be registered with Clinical Trials Registry ([www.clinicaltrials.gov](http://www.clinicaltrials.gov)), before recruitment is initiated after IRB approval.

## DILAPAN-S® Hygroscopic Cervical Dilator

### Instructions for Use

#### GENERAL INFORMATION

[figure not shown]
##### Content

A sterile hygroscopic cervical dilator packed in a printed composite primary peel-open pouch, a piece of Instructions for use.

The DILAPAN-S® is available in a box of 25 dilators and in the following dimensions: 4x65 mm, 4x55 mm, 3x55 mm.

